### **5.1. Data Purpose**

The Recipient will have access to the Data Set to the extent necessary for the purpose of the Study. The pseudonymized Data Set shall be made available only to the Party responsible for Statistical Analysis. The Data Set will not be disclosed, transferred, or made available to any other third party. Summary Safety data may be transferred to the Manufacturers; however, this will NOT include any personal patient data. The Data Set will be kept confidential, and all reasonable steps will be taken to protect it against accidental or unlawful loss, modification or destruction, or unauthorized access, disclosure, copying, use, misappropriation, or modification. Following study closure, datasets cannot be transferred to any third party without the permission of the Recipient.

The results will be published in an academic publication. The Study Sites will be informed about the publication, and the publications will be uploaded to the EUBREAST website, the link to this publication will be sent to Study Sites. In accordance with customary scientific practice, any publications or presentations made in relation to the results, whether in oral, visual, or written form, the Study Site will be acknowledged as the source of the Data Set (see section “Publication and authorship policy”).

### **5.2. Data Ownership**

The data is submitted by the Provider with the intention of contributing to a combined dataset. Providers can access their Study Site’s complete dataset at any point within the study recruitment period.

## **6. Publication and authorship policy**

All presentations and publications will be made on behalf of the EUBREAST Study Group. Two levels of authorship are proposed based on degree of study participation:

### **6.1. Named authors**

Named authors will be required to meet the International Committee of Medical Journal Editors (ICMJE) criteria ([www.icmje.org](http://www.icmje.org)) for authorship. These will include:

- Principal Investigator and Deputy Principal Investigator
- Members of the Steering Board
- Heads of National Steering Committees representing countries with top recruiter status
- Main statistician

### **6.2. Acknowledged collaborators**

Collaborators will have made a considerable contribution to the study but will not have met the ICMJE criteria for authorship (non-author contributors). These will include:

- Heads of National Steering Committees representing countries without top recruiter status
- Members of National Steering Committees
- Local PIs of active Study Sites who have recruited at least one study participant. Recruitment in this context includes submission of a completed data set. In case a Study Site enrolled more than ten patients, an additional member of the Study Site will act as acknowledged collaborator. In case a Study Site enrolled more than fifty patients, two additional members of the Study Site will act as acknowledged collaborators.

All acknowledged collaborators will be listed as GRAMAREG Study Group.

## **7. Statistical considerations**

Data analysis will be descriptive only.

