## **4. Methods**

### **4.1. Study design**

Investigator-initiated non-interventional observational international prospective / retrospective cohort study

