### **4.2. Aims and objectives**

#### Primary outcomes:

- Proportion of patients presenting with specific symptoms (e.g., pain, redness, palpable mass)
- Duration of symptoms depending on treatment strategy

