#### Secondary outcomes:

- Type and duration of systemic treatment
- Number of surgeries, if performed
- Recurrence rate
- Risk factors associated with recurrence
- Time between first symptoms occurring and first histological confirmation
- Presentation on breast imaging (mammography, sonography, MRI, if performed)

The analysis of outcomes regarding diagnostics and ultrasound will be performed by the International Steering Committee GRAMAREG-*sono*.

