##### **Retrospective data collection:**

Collection and analysis are performed via an anonymized electronic database maintained by EUBREAST e.V. The participating Study Sites commit themselves to identification and documentation of patients with histologically confirmed idiopathic granulomatous mastitis treated during the investigational period at their institution (i.e., between 1st January 2015 and activation of Study Site). No patient identifying information will be disclosed or documented. Data collected during the retrospective phase of the study will be fully anonymous. The retrospective data will not include prospective follow up.

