##### **Prospective data collection:**

All patients with histologically confirmed idiopathic granulomatous mastitis presenting at the Study Site after activation of the study will be informed about the possible participation in the GRAMAREG registry. The inclusion and exclusion criteria are verified by the investigator and written informed consent is obtained from the patient.

Diagnostic management and treatment should be conducted according to institutional standards. Since the GRAMAREG study is a non-interventional trial, the Study Sites do not deviate from their own institutional protocol at any timepoint.

[figure not shown]
The follow up on patient status is conducted 1, 3 and 5 years after the first diagnosis. In order to collect follow up data the patients will be contacted directly by the study site to evaluate current symptoms (follow up after 1 year) and to document a potential recurrence of IGM (follow up 1, 3 and 5 years after the first diagnosis).

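### Section 7 confines the analysis to description, yet Section 4.2 promises risk factors for recurrence in a registry where follow-up is unequal by design

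*Protocol*

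**What the plan says.** Section 4.1 describes the design as an "Investigator-initiated non-interventional observational international prospective / retrospective cohort study". Among the secondary outcomes in Section 4.2, "Recurrence rate" and "Risk factors associated with recurrence" are separate items. No time horizon is given for either.

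Section 4.4 sets up two data collections. The retrospective one covers patients treated from 1 January 2015 until the site is activated, and there "The retrospective data will not include prospective follow up". For prospective patients, "The follow up on patient status is conducted 1, 3 and 5 years after the first diagnosis", and recurrence is documented at each of those contacts. Section 4.6 leaves the registry open-ended.

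The whole of Section 7 is: "Data analysis will be descriptive only".

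**The concern.** The recurrence rate can be described. Risk factors are a different kind of outcome, because the term claims that a characteristic goes with more or less recurrence once other explanations have been considered. Section 7 does not leave that analysis open for a later statistical analysis plan. The word *only* is a restriction: an analysis plan with a regression model would contradict the protocol, and one that obeys the protocol would have no model for the associations.

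This matters because time at risk differs between patients. A characteristic or treatment that is more common in whichever cohort has been observed longer will tend to show more recurrences even if it has no effect, and a real risk factor can be masked in the same way. Treatment follows institutional standards, so it varies with site and may vary with severity, which is a second source of false associations.

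**Working it through.** **Comparison of the text.** Section 4.2 asks for associations with recurrence and Section 7 permits description. Section 4.4 gives the two cohorts different follow-up, and Section 4.6 means that prospective patients will also differ in follow-up at any data cut. The protocol mentions neither censoring nor adjustment, and does not say whether the cohorts are analysed together or apart.

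**Size, illustration only.** The protocol states no recurrence risk, sample size or follow-up distribution, so there is no figure to reproduce. Every input below is an assumption except the five-year horizon, which is the last planned contact.

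- Five-year recurrence risk 25%, constant hazard h = −ln(0.75)/5 = 0.0575 per year.
- Risk by time t is 1 − exp(−h·t): 5.6% at 1 year, 15.9% at 3 years, 25.0% at 5 years.
- Cohorts of equal size; prospective patients all observed for 5 years; retrospective charts covering 1 or 3 years.
- A factor with no effect, present in a share p of prospective and 1 − p of retrospective patients.

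With R the risk over the chart period, crude recurrence in the pooled cohorts is

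- exposed: p × 25% + (1 − p) × R
- unexposed: (1 − p) × 25% + p × R

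| p / (1 − p) | Chart follow-up | Exposed | Unexposed | Crude RR (truth 1.0) |
|---|---|---|---|---|
| 80/20 | 1 year | 0.8 × 25 + 0.2 × 5.6 = 21.1% | 0.2 × 25 + 0.8 × 5.6 = 9.5% | 2.2 |
| 80/20 | 3 years | 0.8 × 25 + 0.2 × 15.9 = 23.2% | 0.2 × 25 + 0.8 × 15.9 = 17.7% | 1.31 |
| 60/40 | 1 year | 0.6 × 25 + 0.4 × 5.6 = 17.2% | 0.4 × 25 + 0.6 × 5.6 = 13.4% | 1.29 |
| 60/40 | 3 years | 0.6 × 25 + 0.4 × 15.9 = 21.3% | 0.4 × 25 + 0.6 × 15.9 = 19.5% | 1.09 |
| any | 5 years | 25% | 25% | 1.0 |

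If the factor is instead more common in the retrospective cohort, the ratios invert: 1/2.2 is about 0.45 and 1/1.09 about 0.91.

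**Confounding, a separate mechanism.** Take equal follow-up and a factor with no effect, but let 70% of exposed and 30% of unexposed patients have severe disease. With assumed recurrence risks of 30% in severe and 15% in mild disease, crude recurrence is 0.7 × 30 + 0.3 × 15 = 25.5% against 0.3 × 30 + 0.7 × 15 = 19.5%, a ratio of 1.31. Risks of 40% and 10% give 31% against 19%, a ratio of 1.63. Accounting for follow-up time would not remove this.

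**The case against.** The strongest reply is that descriptive does not mean crude. Kaplan-Meier estimates, rates per person-year and tables by cohort, site or treatment are commonly regarded as descriptive, and choosing among them is the business of an analysis plan. Section 7 may mean no more than that nothing will be tested in a confirmatory way. This stands. A reader might infer that Section 7 forces side-by-side percentages from pooled cohorts, but the protocol does not say so, and Section 4.4 describes the two collections separately.

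A reader might also infer that the prospective cohort is the one followed longer. That is not established either. Retrospective charts may go back to 2015, and in an open registry many prospective patients may be well short of five years at a given data cut.

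Finally, this is one of six secondary outcomes in a non-interventional registry that states no hypothesis test or decision rule.

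What remains is the conflict of wording. Kaplan-Meier curves by cohort would deal with much of the unequal follow-up, but they do not give adjusted associations for several correlated factors. Cross-stratifying by more than one or two factors would soon leave very small groups in a disease this rare. Nor does the protocol commit to any method that takes account of follow-up time.

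**Conclusion.** The conflict between Sections 4.2 and 7 is real and has to be settled in the protocol, because an analysis plan cannot lift a restriction that the protocol imposes. It should be fixed, but it is not critical: it limits what the registry can conclude about one secondary outcome and leaves the recurrence rate reportable.

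The size and direction of any distortion cannot be derived from the protocol. Under the stated assumptions a null factor shows a crude relative risk of 1.09 to 2.2, or about 0.45 to 0.91 with the imbalance reversed, and 1.0 with equal follow-up. The value of 2.2 is one strong scenario and should not be read as an expected bias. All of these figures presuppose a pooled crude comparison, which the protocol neither plans nor excludes. It would also go too far to say that nothing useful about recurrence can be learned descriptively. What cannot be delivered is a set of adjusted associations that would justify the term risk factors.

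**What to change.** Choose one of two wordings at the next protocol version.

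(a) Amend Section 7: *Analysis is descriptive, except that factors associated with recurrence are estimated in an exploratory time-to-event analysis. This accounts for censoring and for ascertainment of recurrence at 1, 3 and 5 years, is stratified by retrospective or prospective cohort, and uses a short list of factors fixed in advance. Results are reported with 95% confidence intervals.* The model and any provision for few events can be left to the analysis plan. The reference to ascertainment is needed because a recurrence first learned of at a scheduled contact may be dated only to the interval since the previous one.

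(b) Keep Section 7 and reword the outcome in Section 4.2: *Recurrence by patient characteristics, by cohort, with Kaplan-Meier estimates at 1, 3 and 5 years*, dropping the term risk factors. This suits a sponsor who deliberately wants description and no model.

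The cost is a sentence and modest extra analysis. Either route needs dates of recurrence and of last contact. The case report form is not shown, so the sponsor should confirm that it captures them, above all for the retrospective records: these are fully anonymous under Section 4.4, and a missing date may not be recoverable later.

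In the same amendment, check the primary outcome "Duration of symptoms depending on treatment strategy" against Section 7. It can be reported descriptively by treatment group, but treatment is not allocated, so the text should say whether any comparison between strategies is intended.

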## **8. Safety**

GRAMAREG is a non-interventional study. All diagnostic and therapeutic procedures will be conducted according to institutional standards in the clinical routine.

## **9. Funding**

Study support is currently applied for.

## 11. Protocol Change Log

| Version | Changes   |
|---------|---|
| 1.4     | 
Members of the Steering Board updated ([name] [name], [name] [name], [name] and [name] added)
 
International Steering Committee GRAMAREG-sono added
 
Corrected scientific title of [name]
 
Literature updated (Krawczyk et al. Cancers 2024)
 |
| 1.3     | 
Addition of "diagnostic features" to the study tittle
 
Rationale for inclusion of cystic neutrophilic granulomatous mastitis (CNGM) specified
 
Inclusion criteria expanded to include CNGM
 
Study flow chart corrected
   |
| 1.2     | 
Members of the Steering Board updated ([name]. [name] added)
 
Protocol change log added
  |
| 1.1     | Follow up described in more detail  |
